### **Specific Aim 2: Exercise Tolerance in Obese Children**

Introduction: Exercise Tolerance. The *working hypothesis* is that respiratory effects of obesity in children will decrease exercise tolerance (i.e., decreased peak  $\dot{V}O_2$  in ml/min/kg) but **not**

cardiorespiratory fitness (i.e., normal peak  $\dot{V}O_2$  in percent predicted based on ideal body weight), except in those misdiagnosed with asthma. The *rationale* behind the proposed research centers on the fact that conventional thinking suggests that obese children are 'out of shape' or deconditioned, but when displayed appropriately, cardiorespiratory fitness will be within normal limits during graded cycle ergometry. However, in obese children misdiagnosed with asthma, cardiorespiratory fitness may be decreased also due to respiratory symptoms and/or avoidance of exercise.

Methodology, experimental protocol and measurements. The strategy will be to measure HR, BP, SpO2%, PETCO2, gas exchange ( $\dot{V}_E, \dot{V}O_2, \dot{V}CO_2$ , RER), RPB (Borg 0-10 scale), RPE (6-20 scale), and breathing mechanics (IC, EELV, EILV) including breathing pattern and tidal flow-volume loops continuously during maximal graded cycle ergometry (step increments of 10W/min) using standard methods as required for participant safety. A maximal flow-volume loop will be measured before and immediately after the exercise to assess the possibility of bronchodilation or bronchoconstriction (i.e., exercise induced airway reactivity) during exercise.

Peak exercise capacity will be evidenced by peak HR, peak work rate, peak  $\dot{V}O_2$ , and peak RER obtained during graded cycle ergometry as well as by verification at 105% of maximal work rate to exhaustion.

Expected results. We expect that in comparison with nonobese children, obese children will have decreased exercise tolerance due to increased body weight but normal cardiorespiratory fitness when peak  $\dot{V}O_2$  is properly evaluated, despite altered breathing mechanics (e.g., EELV, expiratory flow limitation) during peak exercise. However, we also expect cardiorespiratory fitness may be decreased in obese children misdiagnosed with asthma. We also expect to have a better understanding of obesity-related alterations in respiratory function during peak exercise in obese children and the differences (if any) between obese boys and girls.

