#### **Specific Aim 4: Effects of Weight Loss and Regular Exercise and Weight Gain in Obese Children**

Introduction. The *working hypothesis* is that weight loss (or an equivalent reduction in BMI percentile) and regular exercise will improve respiratory function, exercise tolerance, and DOE in obese children, including obese children misdiagnosed with asthma, while continued weight gain (or increase in BMI percentile) will worsen respiratory function, exercise tolerance, and DOE in obese children, including obese children misdiagnosed with asthma, as compared with normal weight children after 1 yr. The *rationale* behind the proposed research centers on the fact that FRC at rest, EELV during exercise, and peak  $\dot{V}O_2$  in ml/min/kg will be increased in obese children after weight loss and regular exercise but decreased by continued weight gain. The cumulative effect of the weight loss program would thereby reduce the potential for breathing limitations at rest and/or during exercise, increase exercise tolerance, and potentially reduce DOE in obese boys and girls, including those misdiagnosed with asthma, but weight gain would have the reverse effects.

Methodology, experimental protocol and measurements. The strategy will be to repeat the measurements detailed in Aims 1-3 after 1 yr: 1) in 12 obese boys and 12 obese girls after weight loss (or an equivalent reduction in BMI percentile) and regular exercise, 2) in 12 obese boys and 12 obese girls after weight gain (or an increase in BMI percentile), 3) in 12 obese boys and 12 obese girls misdiagnosed with asthma regardless of weight changes or exercise participation, and 4) in 12 normal weight boys and 12 normal weight girls. We will test at 1 yr because parents **prefer** to have testing done during summer vacation months only.

*Weight Loss and Regular Exercise* will be prescribed by attending physicians at the **COACH**

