Expected results. We expect that a program of weight loss (or an equivalent reduction in BMI percentile) and regular exercise will increase FRC at rest and EELV during exercise while weight gain will decrease these. The change in FRC and EELV may be correlated with changes in body composition (if any). These improvements in respiratory function and breathing mechanics may also be associated with decreased DOE as well, while weight gain would have the reverse effects. Exercise tolerance will be increased in ml/min/kg but we expect no change in cardiorespiratory fitness (i.e., Peak  $\dot{V}O_2$  as percent predicted based on ideal body weight), which may actually be slightly decreased, including those misdiagnosed with asthma. With weight gain, exercise tolerance will be decreased but cardiorespiratory fitness would be unchanged as well. We also *expect* to have a better understanding of the importance of weight loss and regular exercise and weight gain on respiratory function and breathing mechanics in obese children, and the differences (if any) between obese boys and girls.

Interpretation of results. We will interpret these results to suggest that weight loss (or an equivalent reduction in BMI percentile) and regular exercise will have a significant improvement on respiratory function, exercise tolerance, and DOE, while weight gain will worsen respiratory function, exercise tolerance, and DOE in obese children all through a common mechanism of increasing or decreasing EELV. Weight loss may also reduce potential clinical breathing limitations at rest and during exercise (e.g., expiratory flow limitation) but weight gain would increase limitations. This would be important knowledge for healthcare providers who may not appreciate the obesity-related respiratory effects in obese children, and who may assume that

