### **Statistical Considerations**

Co-investigator [name] (UT Southwestern Division of Biostatistics) is the statistical co-investigator on this project and has assisted in the development of the statistical plan; she will also

Total n=96	Obese	Obese misdiagnosed with asthma	Non- obese
Boys	n=24	n=12	n=12
Girls	n=24	n=12	n=12

direct the data analysis on an on-going basis.

Statistical Plan. Our plan is to complete testing in nonobese and two obese groups, boys and girls separately but concurrently. Thus, sample size calculations are based upon within-gender comparisons per allocation in table at right. In Aims 1-3, comparisons will be made between nonobese, obese, and obese children misdiagnosed with asthma within the same gender with analysis of variance models (ANOVA). Pairwise group comparisons will be made using least squares means contrasts derived from the linear models. Data transformations or nonparametric tests will be utilized as needed to meet analysis assumptions. At baseline, ISSAC and ECRHS asthma screening questionnaire scores will be compared among groups with the Kruskal-Wallis test. Comparisons for Aim 4 will be made similarly, but with the addition of repeated measurements to assess the two obese groups and the nonobese children of the same gender at baseline and at 1 year of follow-up. Additional assessments of gender effects will be performed as part of a secondary analysis, but we are not powering the study to detect interaction by gender. Alpha is set at 0.05 for ANOVA and planned contrast power (PASS 11, NCSS, LLC, Kaysville, UT), described below . Data will be analyzed using SAS version 9.4 (SAS Institute, Inc., Cary, NC).

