**Aim 4.** Primary variables for Aim 4 are change in FRC at rest, peak  $\dot{V}O_2$ , RPB, and EELV during constant load exercise from before to after 1 year of follow-up. We are gaining experience with studies in children; current preliminary data from n=7 obese children yield similar mean differences and standard deviations as in adults. Therefore, based upon the change in EELV during constant load exercise in obese men before ( $35 \pm 5$ ) and after ( $39 \pm 3$ ) a loss of 13% of body fat, and the change in RPB during constant load exercise in obese women before ( $4.7 \pm 1.1$ ) and after ( $3.2 \pm 1.6$ ) weight loss, our sample will have sufficient power (.80,  $\alpha=0.05$ ) to detect meaningful paired differences (e.g., 1.5 in RPB) with weight loss and regular exercise. We will retest all children after ~1 yr. We expect less than 10% attrition and repeated data on nearly all children will be available for this Aim. Combining the two obese groups (with and with asthma misdiagnosis), the children will be divided into obese who lost weight, obese who gained weight, and control normal weight children and respiratory changes will be compared between groups with ANOVA as described for Aims 1-3. While these categorized weight changes have clinical appeal, weight change analyzed as a continuous variable may be more powerful and informative. Hence, change at 1 year minus baseline will also be evaluated with Spearman or Pearson correlations to quantify the association between 1-year weight change and the change for respiratory function, exercise tolerance, and DOE variables and, with the 36 obese participants analyzed (by gender), a correlation of 0.45 can be detected with 80% power.

To evaluate gender effects, baseline and follow-up measurements for FRC, peak  $\dot{V}O_2$ , RPB, and EELV will be analyzed in mixed-effects repeated measures models with the study participant included as a random effect. Interactions between gender, study group (obese, obese misdiagnosed with asthma, nonobese), and time can be assessed as fixed effects; weight change effect will be modeled as a covariate. PAQ-C score changes will also be assessed with repeated measures models.

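### Aim 4 relates weight change to peak VO2 per kilogram without assigning a peak VO2 scale, so part of any association comes from the denominator and cannot by itself support the EELV explanation

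*Combined protocol and SAP*

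**What the plan says.** Specific Aim 4 (Introduction) expects that peak VO2 "in ml/min/kg will be increased in obese children after weight loss and regular exercise but decreased by continued weight gain". Its Expected results again put exercise tolerance in ml/min/kg, and treat cardiorespiratory fitness (percent predicted for ideal body weight) as a separate index that should not change and may fall slightly.

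Specific Aim 2 makes the same separation. It expects that "obese children will have decreased exercise tolerance due to increased body weight but normal cardiorespiratory fitness when peak" VO2 is properly evaluated.

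Statistical Considerations, Aim 4, names change in peak VO2 among four primary variables but gives no unit for it. Weight change is then used in three places:
- **Categories.** For the ANOVA, "the children will be divided into obese who lost weight, obese who gained weight, and control normal weight children". The sentence goes on to speak of comparing respiratory changes.
- **Correlations.** These quantify "the association between 1-year weight change and the change for respiratory function, exercise tolerance, and DOE variables".
- **Mixed model.** Baseline and follow-up values are modelled with a random participant effect. "Interactions between gender, study group (obese, obese misdiagnosed with asthma, nonobese), and time can be assessed as fixed effects"; then "weight change effect will be modeled as a covariate". This model serves gender effects, and the Statistical Plan says "Additional assessments of gender effects will be performed as part of a secondary analysis".

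The Aim 4 Interpretation would read the findings as weight loss improving, and weight gain worsening, respiratory function, "exercise tolerance, and DOE in obese children all through a common mechanism of increasing or decreasing EELV".

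**The concern.** Peak VO2 in ml/min/kg is absolute peak VO2 divided by body weight. Relating its change to weight change puts weight on both sides. A child who loses weight and delivers exactly the same oxygen uptake gains ml/min/kg, and a child who gains weight loses it. A finding that tolerance rose in those who lost weight is therefore what division alone would produce. It can appear when absolute peak VO2 is unchanged or has fallen. Read under the Aim 4 interpretation, it would count as evidence of a respiratory benefit acting through EELV. A ml/min/kg result cannot carry that claim alone.

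A smaller point concerns the mixed model. Its outcomes are levels at two visits. If weight change enters as one value per child with no time term, its coefficient describes the average level over both visits, not the 1-year change.

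**Working it through.** **1. The plan's own figure.** Statistical Considerations, Aim 4, states 80% power for r = 0.45 with 36 obese children per gender. By Fisher's z, two-sided alpha 0.05 (sidedness assumed): atanh(0.45) × √33 − 1.96 = 0.485 × 5.745 − 1.96 = 0.82, and Φ(0.82) = 79.5%. The figure reproduces and is not in question.

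**2. Denominator arithmetic.** Input: obese boys 26.3 ml/min/kg (Statistical Considerations, Aim 2). The 10% loss is the weight programme's initial target (Aim 4 methodology), not an expected study mean. The gains, and the 5% case, are assumptions. Absolute VO2 is held constant.
- 10% loss: 26.3/0.9 = 29.2, a rise of 2.9. 10% gain: 26.3/1.1 = 23.9, a fall of 2.4. Gap 5.3.
- 5% each way: 1.38 + 1.25 = 2.6.

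For scale, the Aim 2 power calculation calls a between-group difference of 4.7 ml/min/kg clinically relevant.

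**3. Induced correlation.** Let sW be the SD of relative weight change, sA the SD of relative change in absolute VO2, and ρ their correlation. Relative change in ml/min/kg is approximately the difference between the two relative changes, so

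r ≈ (ρ·sA − sW) / √(sA² + sW² − 2ρ·sA·sW).

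Inputs from the documents: the example child in Anticipated problems spans about 47.2 to 70.3 kg (104 to 155 lb), midpoint 58.75 kg. Weight change is centred at zero because half the preliminary obese children lost and half gained (Subject Selection). Assumed: weight-change SD 3 to 7 kg, so sW = 3/58.75 = 5.1% to 7/58.75 = 11.9%; VO2 CV 5 to 12% per visit, so sA = √2 × CV = 7.1% to 17.0%.
- ρ = 0, 3 kg, 12%: −5.1/√(5.1² + 17.0²) = −0.29.
- ρ = 0, 7 kg, 5%: −11.9/√(11.9² + 7.1²) = −0.86 (simulation −0.84).
- ρ = 0.3, 3 kg, 12%: numerator 5.1 − 5.1 = 0, so r is about 0.
- ρ = 0.5, 3 kg, 12%: (8.5 − 5.1)/15.1, about +0.22.

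Simulation with 36 obese children per gender over the whole grid:

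| ρ | mean r, ml/min/kg | lost minus gained, ml/min/kg |
|---|---|---|
| 0 | −0.29 to −0.84 | +2.2 to +5.2 |
| 0.3 | −0.01 to −0.80 | +0.05 to +4.3 |
| 0.5 | +0.22 to −0.79 | −1.4 to +3.7 |

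At ρ = 0 the correlation is significant in 42 to 100% of data sets, against 5 to 6% for absolute VO2. At ρ = 0.3 the lost-minus-gained contrast in absolute VO2 is −52 to −128 ml/min, so the two scales point in opposite directions.

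**4. Mixed model on ml/min/kg.** At ρ = 0 the weight change × time slope is −0.49 to −0.55 per kg. This pools controls at an assumed 35 kg. For obese children alone, 26.3/58.75 gives about −0.45 per kg.

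**5. Coding of weight change (any outcome).** Let g be the slope of baseline level on later weight change W, and b the slope of the 1-year change on W. Baseline contributes gW and follow-up (g + b)W, so the two-visit mean contributes (g + b/2)W. A main effect therefore estimates g + b/2. The documents give neither slope. With assumed b = −0.4 and g = −0.2, 0 or +0.2, the main effect is −0.40, −0.20 or 0.00. With b = 0 it equals g. Weight change × time recovers b. With complete data, adding the main effect leaves the gender and group time terms unchanged. Coding W as 0 at baseline and its 1-year value at follow-up gave −0.37 to −0.43 against a true −0.40.

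**The case against.** The strongest reply is that the plan already knows this. It separates tolerance from fitness, attributes lower tolerance to body weight, predicts that ml/min/kg will rise while percent predicted does not, and repeats the same exercise test at 1 year, so both scales will be available. It also allows that EELV might change without associated changes in tolerance. That much stands, and it narrows the point to two gaps. The statistical section does not say which scale enters the Aim 4 analyses. The interpretation attributes changed tolerance to EELV although the expected results foresee no change in fitness.

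It can also be said that the ANOVA sentence mentions only respiratory changes. That is why the ANOVA is included here only if it covers peak VO2; the correlation names exercise tolerance outright. If children were classified by BMI percentile, which Aim 4 allows as an equivalent of weight loss, the coupling would take a different size, which was not modelled.

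On the covariate, the reply is largely right. The model is secondary and aimed at gender, its time terms are unaffected with complete data, and the correlations and ANOVA work on change. The wording excludes neither a time interaction nor a coding that is 0 at baseline.

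**Conclusion.** The point holds for one of the four Aim 4 primary variables, peak VO2 in ml/min/kg. On that scale an association with weight change is expected from the denominator, and it cannot alone support a physiological or EELV-mediated conclusion. The coupling is arithmetic. Its size is not determined by the documents: it rests on assumed weight-change SDs, VO2 variability and ρ, and it ranges from well beyond the planned detectable 0.45 to nothing, or to the opposite sign.

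Three stronger readings are not supported:
- A reader might infer that every Aim 4 weight-change analysis is affected. FRC and EELV in %TLC, and RPB on the Borg scale, have no body weight in their units.
- A reader might infer that a spurious significant correlation is certain. At ρ = 0.3 or 0.5 it can disappear.
- A reader might infer that the mixed model is wrong. It is unspecified, which is a matter of missing detail.

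**What to change.** 1. In every Aim 4 analysis relating peak VO2 to weight change (correlation, mixed model, and the lost/gained/control ANOVA if it includes peak VO2), also analyse absolute peak VO2 in ml/min or the plan's own percent predicted for ideal body weight.
2. Base any physiological or EELV-mediated claim on that measure. Report ml/min/kg results as including the weight denominator, and align the Aim 4 interpretation with this.
3. Minor: state how weight change enters the secondary mixed model. If it is one value per child, take weight change × time, or an equivalent coding that is 0 at baseline, as the weight-change effect. Keep the model without it for the unadjusted gender × time and group × time effects, because adding it makes those terms conditional on weight change.

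The cost is SAP wording, a parallel set of peak VO2 analyses, and a few degrees of freedom in one secondary model. Both alternative scales come from the exercise test already planned.

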#### **Anticipated problems and potential solutions**

The anticipated changes in respiratory function (particularly FRC) should be apparent at this level of obesity. A 10.5 yr old boy at 4' 8 1/2" or 143.3 cm at the 95th percentile will have a body mass of 103-105 lb. The upper limit for that same child at 150% of the 95th BMI percentile is 155 lbs. Thus, the range for this example child is ~50 lbs (22.7 kg). This increase in weight is significant and should produce the type of effects we expect as confirmed in our preliminary data. However, if this does not hold true, we do not believe increasing the range of obesity to include those with BMI scores > 150% of the 95th percentile would yield a subject population that is representative of the majority of obese children. We intend to perform testing for Aims 1a and 1b in two sessions ( $\approx 2.5$  hr each). This approach has been very attractive to the children and parents without complaint and the children have performed upright and supine respiratory function tests without difficulty. Also, if the weight placed on the abdomen is not tolerable, we will investigate other methods like a weighted vest or broader distribution of the weight over the chest wall. We have not found our standard graded cycle ergometry protocol to be a problem when testing peak performance in obese or nonobese children, especially when confirmed at supra-maximal work rates. However, if we find the protocol difficult for them, we can try different stage increments, or try a non-continuous exercise test to determine peak exercise capacity. Also, we believe that the level of obesity planned for this study will not preclude the obese children from completing exercise testing at 30 or 40W as in the nonobese children or with our ability to examine respiratory function, breathing mechanics, and DOE during exercise at 30 or 40W. Nevertheless, we will complete a second exercise session at 50% of peak  $\dot{V}O_2$  just to be sure. So far all procedures and testing has been very well-tolerated and without complaint. Weight loss success is always a concern that involves many personal and family-related issues.

However, all of the investigators are aware of these difficulties and have the insight and flexibility to try different techniques to overcome obstacles that may arise. However, by testing the participants who are not successful with weight loss but actually gain weight, we believe we have dramatically increased the value of Aim 4. However, some subjects may have no change in body composition or %body fat. We anticipate this will not occur very often since all children will gain weight, fat weight, and/or fat free weight over the course of 1 yr.

#### **Tentative Timetable**

It will take  $\approx$ 5 yr to complete the proposed studies. Roughly 30 to 60 children will be studied each year. Starting in year two, half will be repeat studies and half will be new participants. The last year will be devoted mostly to repeat studies. All projects will run concurrently but most of the data collection will take place in the summers with the exception of the obese children with respiratory symptoms misdiagnosed with asthma. These children may be able to complete testing throughout the year. We are highly confident that we can successfully complete this extremely important but ambitious project in 5 yr as planned.
